IRB Application for Population Health and Quality Research Study

Title of Study: Combined administration of Bupivacaine and Exparel versus Bupivacaine or Exparel alone for postoperative analgesia in posterior lumbar spine surgery - A Prospective Randomized Study

Background and Statement of Context

It is estimated that 1 million elective (inpatient and outpatient) spinal surgery procedures are performed each year in the US, including 464,000 spinal fusions, 342,000 discectomies, and 213,000 laminectomies [1, 2]. Spine surgery is thought to result in severe postsurgical pain for a variety of reasons, including the size of the incision, the damage that may occur to ligaments, muscles, bone, discs, and joints when performing the surgical procedure, the existence of preoperative pain, and opioid-induced hyperalgesia (OIH) that may occur with pre-operative opioid use [3]. OIH may result in sensitization of the dorsal horn of the spinal cord where pain signals are first processed, reducing the threshold required to perceive pain, thereby prolonging and magnifying its effect [4]. Pain following spine surgery is thought to be most intense after a few hours, gradually subsiding over a few days, as supported by pain severity scores recorded in studies of various approaches to managing postsurgical pain [5]. Uncontrolled postsurgical pain results in delayed mobilization and consequently longer length of hospital stay (LOS) and morbidity associated with bed rest, increased opioid usage, and lower patient satisfaction.

A variety of approaches are currently used to manage postsurgical pain, including pre-emptive analgesia, systemic analgesia, regional analgesia, and local analgesia [6]. These approaches are often combined in a multimodal regimen intended to address the various components of postsurgical pain, including nociceptive, neuropathic, and inflammatory mechanisms [7]. Many of the current approaches to managing postsurgical pain require use of opioid analgesics such as morphine, fentanyl, hydromorphone, hydrocodone, or oxycodone [8]. Many of these approaches provide only temporary pain control since the medications used have a short duration of effectiveness [9, 10]. Repeated or continuous dosing is therefore necessary to extend their effectiveness, which must be administered by clinical staff (e.g. IV or IM bolus), Patient Controlled Analgesia (PCA) device, elastomeric pump, or taken orally when permitted (e.g. after regaining gastrointestinal motility).

Although short-term opioids can be effective to manage moderate to severe pain, they are associated with a variety of opioid related adverse events (ORAEs), including potentially incapacitating side effects and serious adverse events. For postsurgical pain, patients are at greatest risk for ORAEs during the first 24 hours after surgery when their opioid use is highest [11]. The use of opioids to manage postsurgical pain may be of particular concern for spine surgery, since many patients are already using opioids prior to their surgical procedure. This increases the possibility of ORAEs with higher perioperative doses and continued use beyond the perioperative period [3]. In addition, consumption of opioids is often an outcome measure in spine surgery, and continued or increased use is considered an indicator that the surgical procedure was not successful [12]. It may therefore be beneficial to minimize the amount of opioids consumed for postsurgical pain.

Given the limitations of current approaches to managing postsurgical pain, as well as the consequences of not adequately managing pain following surgical procedures, researchers are continually developing and investigating new approaches that provide optimal pain management. Postsurgical pain management regimens are also being evaluated and refined as a component of broader enhanced recovery after surgery (ERAS) initiatives intended to improve outcomes, reduce hospital LOS, and promote return to normal activities following elective surgical procedures [13]. These initiatives generally favor approaches to manage postsurgical pain that may increase early ambulation and discharge (e.g. regional or local analgesia with local anesthetics) while discouraging those that may decrease them (e.g. IV PCA with opioids).

Approved by the FDA in 2011, Exparel (liposomal bupivacaine) is a sustained-release version of the local anesthetic bupivacaine. While bupivacaine may last 6 to 12 hours to provide post-surgical relief, it is claimed that Exparel can last up to 72 hours after local infiltration at the surgical site [14]. Different studies have also compared the efficacy of Exparel to bupivacaine for the management of postsurgical pain following various surgical procedures, including inguinal hernia repair, breast augmentation, and TKA [15-20]. While some of these studies have supported the efficacy of Exparel to provide superior relief of postsurgical pain, others have found bupivacaine to be just as effective [20]. There is still however, a paucity of literature on the efficacy of Exparel for spine surgery pain management.

Study Questions/Objectives and Hypothesis

This study is aimed at prospectively examining clinical and economic outcomes when managing postsurgical pain using local infiltration of Exparel for patients undergoing primary, 1 or 2 level, lumbar laminectomy with or without fusion. There is a growing body of evidence suggesting that combining Exparel with a short acting numbing medicine gives much better pain coverage. The rationale is that Exparel can take several hours to have anesthetic onset and conventional thinking believes that if we can cover the immediate postoperative pain better with an immediate acting anesthetic to bridge the onset gap, then better outcomes will be achieved. The combination of these medications have been used in various studies previously in other areas of the body both in orthopedics and non-orthopedics and no adverse effects of combining these medications and in similar quantities/dosing have been observed [22,23,24]. To this end, we hypothesize that compared to patients that only received local infiltration of bupivacaine or only administered Exparel, the intervention group treated to a combination of Exparel and bupivacaine would, during their hospital stay following surgery, experience:

- 1. Reduced mean postoperative pain score (Wong-Baker pain faces scale of 0-no pain, to 10-extreme pain)
- 2. Reduced total consumption of opioids (in mean morphine equivalents)
- 3. Reduced overall cost of postoperative pain control medications
- 4. Decreased incidence of ORAEs

- 5. Reduced time to achieve physical therapy discharge criteria (criteria set according to each patient's living situation, preoperative physical function, comorbidities, and other goals)
- 6. Reduced inpatient length of stay (LOS)

Study Benefits to Virtua

This study could potentially benefit Virtua in several ways. If Exparel is shown to reduce postoperative pain for spine surgery patients, and consequently reduce their opioid consumption for postoperative pain management, then there could be the potential to see an improvement in patient satisfaction with regards to pain management. In addition, Virtua could stand to gain some cost savings if Exparel is shown to support decreased incidence of ORAEs such as respiratory depression, leading to reduced time to physical therapy discharge criteria and consequently reduced LOS.

If on the other hand, the study indicates that the more expensive Exparel is no more effective at managing postoperative pain compared to the cheaper alternatives, then Virtua stands to directly gain significant cost savings by adopting the use of the cheaper options as standard practice.

Study Methodology

Patients who meet all of the following inclusion criteria may be eligible to participate in the study if:

- 1. Age 18 or older;
- 2. Primary indication is low back pain, lumbosacral radiculopathy, lumbar disc degeneration, lumbar disc herniation, stenosis, spondylolisthesis, spondylolysis, or deformity requiring surgical intervention;
- 3. Scheduled to undergo primary, 1 or 2 level, posterior lumbar laminectomy with or without fusion, discectomy with fusion, or fusion at Virtua Memorial Hospital;
- 4. Willing to provide informed consent, participate in study, and comply with study protocol.

Patients who meet any of the following criteria may not be eligible to participate:

- 1. Hypersensitivity or allergy to local anesthetics;
- 2. Pregnant or contemplating pregnancy prior to surgery;
- 3. Previous surgery in lumbar spine (i.e. other than microdiscectomy);
- 4. Prior treatment for alcohol, recreational drug, or opioid abuse;
- 5. Serious spinal conditions (e.g. spinal cord compression, cauda equina syndrome, spinal infection, spinal tumor, spinal fracture, inflammatory or systemic spinal arthritis);
- 6. Surgery involving more than 2 vertebral levels;

- 7. Worker's compensation or personal injury related to lumbar spine (treatment outcomes may be affected by patient's personal interests [21]; could also run into potential issues with reimbursement).
- 8. Lactating women
- 9. Patients with end stage liver disease

During the preoperative office visit, the surgeon will inform patients that appear to meet study eligibility criteria, about the study, and discuss the differences between the three postoperative pain management alternatives, including their potential risks and benefits. The surgeon will make clear to the patient that consenting to be a part of the study means that the patient has agreed to be randomly assigned to one of the three postoperative pain management groups. The patient would be told that the random assignment is going to be determined by rolling a standard die. The patient would be informed that the patient's pain would be controlled regardless of group assignment and that no placebos would be used.

Patients who agree to learn more about the study will be approached by a designated and trained study physician assistant (PA), briefly informed about the study, and asked if they wish to complete the screening questionnaire (Appendix 1) to see if they may be eligible to participate. Once the screening questionnaire is completed by the patient, it will be reviewed by the PA to ask any required clarifying questions and obtain additional information to determine eligibility. Participants who appear to meet eligibility criteria will be reviewed by the PA with one of the study investigators prior to confirming if they are eligible to enroll in the study.

Patients who are deemed eligible to participate in the study and are willing to participate will be asked by the PA to complete the research informed consent. This document will be summarized verbally by the PA and potential participants will be given the opportunity to ask questions about the protocol or their involvement prior to providing consent. Those who agree to participate and provide research informed consent will be enrolled in the study, and given a copy of the research informed consent document. The patient's informed consent would be added to the patient's chart.

On the day of surgery, in the operating room, the circulating nurse will roll a die to randomly assign the patient to one of the three pain management groups. The study intervention group (die roll outcome 1 or 2) will receive a local infiltration of EXPAREL and bupivacaine 0.5% w/v solution into the surgical site (1 level patients – 20 mL Exparel + 30 mL bupivacaine 0.5% w/v solution; 2 level patients – 20 mL Exparel diluted to 40mL + 30 mL bupivacaine 0.5% w/v solution). The two medications will not be combined in the same syringe to minimize the possibility of a direct interaction between the two. While to date, no such interaction has been confirmed, we will maintain a strict "no mixing of bupivacaine and Exparel in the same syringe" policy throughout this study. The second group (die roll outcome 3 or 4) will only be administered local infiltration of Exparel (1 level patients – 20 mL Exparel; 2 level patients – 20 mL Exparel diluted to 40 mL). The third group will be treated to a local infiltration of 30 mL bupivacaine 0.5% w/v solution. Anesthesiologists will use their usual pre-operative and intra-operative techniques for all study participants and both study groups will receive nurse-administered rescue opioids as needed.

The patients and all staff, including hospital nursing staff, case management, and physical therapists, will be blinded as to which pain management treatment the patient received. While the surgical team cannot be blinded because the appearance of the drugs is different, they will however, not be assessing the outcome measures.

The primary outcome in this study will be the mean postoperative pain score derived from the pain scores recorded by the nursing staff in each participant's clinical records using the visual analog scale of 0-no pain to 10-extreme pain, several times in each 24-hour period, for the entire duration of the patient's hospital stay. Adopting [20] assumptions of a target reduction in mean overall postoperative pain scores of 1 point on the VAS and our anticipated variance of 2, it is estimated using one-way analysis of variance that for a statistical power of 80% and significance level of 0.05, a minimum of 40 participants will be required in each study group for a total of 120 study participants. To minimize the possibility of dropouts or incomplete data impacting the analysis, a minimum of 45 participants will be enrolled in each study group, for a total of 135 enrollees.

Secondary outcome measures in this study include total opioid consumption. All opioid analgesics used in the hospital will be recorded in the participant's clinical record, including: Name of medication (e.g. morphine); Dose administered (e.g. 10mg); Route of administration (e.g. IV, IM, oral); Reason for administration (e.g. surgical site pain). All opioid analgesics will be converted into oral mg morphine equivalent to determine the total dose of opioids used during the hospital stay using the conversion factors in Appendix 2. Other secondary outcome measures include mean time to achieve physical therapy discharge criteria, mean LOS, and incidence of ORAEs. ORAEs will be documented using the checklist shown in Appendix 3 with assistance from a nurse during every nursing shift (i.e. every 12 hours) until hospital discharge).

Means will be compared among all the three arms using analysis of variance, proportions will be compared using chi-square tests, and logistic regression will be used to analyze for confounding effects. All statistical analyses will be conducted in Minitab 16 Statistical Software.

Protection of Human Subjects

Throughout the study, the principal investigators (Virtua Memorial spine surgeons and PAs), will be the only ones with access to the data collection database. Following the completion of the study, all personal health information collected, including name, gender, age, significant medical comorbidities, and postoperative complications, will be de-identified as soon as possible prior to data analysis and any subsequent publications or research submissions. Patient would be told participation is purely voluntary with no monetary reimbursement and minimal risk of being assigned to one of the three pain management groups.

References

- 1. Centers for Disease Control and Prevention (CDC). National Hospital Discharge Survey: 2006 Annual Summary. Vital and Health Statistics, 2010;13(168).
- 2. Centers for Disease Control and Prevention (CDC), Health, United States, 2012: With Special Features on Emergency Care. 2012: Hyattsville, MD.

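### The protocol foresees adopting the cheaper drug if Exparel shows no advantage, but the planned omnibus ANOVA gives no interval that could support that conclusion

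*Combined protocol and SAP*

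**What the plan says.** The section Study Benefits to Virtua describes two ways the hospital could gain. The first follows if Exparel reduces pain. The second is conditional on the study indicating that "the more expensive Exparel is no more effective at managing postoperative pain compared to the cheaper alternatives", in which case the saving comes from "adopting the use of the cheaper options as standard practice". The section does not say what result would count as that indication.

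The hypotheses, under Study Questions/Objectives and Hypothesis, are all of superiority: relative to either drug alone, "the intervention group treated to a combination of Exparel and bupivacaine would, during their hospital stay following surgery, experience" less pain, lower opioid use and the other listed improvements. No hypothesis concerns Exparel alone against bupivacaine alone, and none is of equivalence or non-inferiority.

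Study Methodology sizes the trial on "a target reduction in mean overall postoperative pain scores of 1 point on the VAS" with "our anticipated variance of 2", for a "statistical power of 80% and significance level of 0.05". This gives 40 per group, raised to 45 for dropout. The analysis of means is one clause: "Means will be compared among all the three arms using analysis of variance". The section names no pairwise contrast, confidence interval or margin, and gives no guidance on reading a null result.

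**The concern.** The second anticipated use of the trial needs a statement about how large an Exparel benefit could still be. An omnibus F test gives a p-value for whether any of three means differ. It does not estimate Exparel against bupivacaine, and a large p-value can come from no effect or from too little information. A reader of the final report who has only that p-value could take an inconclusive trial as evidence of no benefit, and the protocol has already named the practice change that would follow. At stake is a hospital-wide choice of analgesic made on data that might still be compatible with the benefit the trial was designed to find.

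**Working it through.** **Inputs (Study Methodology).** Target difference 1 point; variance 2, so SD = √2 = 1.414; α = 0.05; power 80%; 40 evaluable per arm (45 enrolled).

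**1. Reproduce the stated sample size.** Three-group one-way ANOVA, largest difference 1 point, third mean midway (the least favourable pattern). Noncentrality λ = nδ²/(2σ²) = 40 × 1/(2 × 2) = 10, on 2 and 117 degrees of freedom. Power = 80.5%, and n = 40 is the smallest size that reaches 80%. The stated figure is confirmed.

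**2. Precision of one pairwise comparison.** SE = √(2σ²/n) = √(4/40) = 0.316. Half-width of the 95% confidence interval = t(0.975, 117) × SE = 1.980 × 0.316 = 0.63 points. At 45 per arm it is 1.978 × 0.298 = 0.59.

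**3. Chance of a non-significant result, 40 per arm.** Pairwise figures use the noncentral t with noncentrality δ/SE; omnibus figures use the noncentral F. The omnibus range runs from one arm differing by δ from both others (lower) to the midway pattern (upper).

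| True benefit | Pairwise | Omnibus |
|---|---|---|
| 0.5 | 65% | 66–73% |
| 0.75 | 35% | 32–46% |
| 1.0 | 12% | 9–20% |

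**4. Non-significant and still compatible with 1 point.** This needs an observed difference between 1 − 0.63 = 0.37 and 0.63.

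- True benefit 0.5: about 31% of all trials, or 47% of the non-significant ones (0.47 × 0.65 ≈ 0.31).
- True benefit 1: about 10% of all trials, or 79% of the non-significant ones (0.79 × 0.12 ≈ 0.095).
- True benefit 0: about 10% of all trials.
- At 45 per arm: about 24% for a true benefit of 0.5, and 6% for 0 or 1.

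**5. What intervals could establish at the planned size.** If there is truly no difference, the chance that a 95% interval excludes a 1-point benefit is 88% for one comparison at 40 per arm. For both Exparel-containing arms together it is about 80% by simulation (the two comparisons share the bupivacaine arm). At 45 per arm the figures are 92% and 86%.

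**6. What excluding 1 point does not establish.** With a true 0.5-point benefit, both intervals exclude 1 point in about 34% of trials if only one Exparel-containing arm benefits, and in about 20% if both do (40 per arm, simulation). So excluding 1 point is not the same as showing no benefit.

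**7. Size needed for other margins.** The documents give no margin, so these are assumptions. To exclude the margin with 80% power at one-sided 0.025 when the true difference is 0: 32 per arm for 1.0 point, 56 for 0.75 and 126 for 0.5.

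**Sensitivity (assumption).** If the SD were 2 rather than 1.414, the half-width at 40 per arm would be 0.89, and a true 1-point benefit would be missed about 40% of the time pairwise.

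**The case against.** The cited sentence is a conditional remark in a section on institutional benefit, not an analysis rule. A reader might infer that the protocol instructs a non-significant result to be read as no benefit, or that a p-value above 0.05 is its only route to that conclusion. The documents do not support either reading. They mention no p-value or threshold at that point, do not commit the hospital to a change, and do not forbid reporting differences with intervals. That part of the objection stands.

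It is also fair that the largest miss rates concern effects smaller than the 1-point target. For the target itself the design performs as stated, and the combination of non-significance with an interval reaching 1 point occurs in only about 10% of trials.

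A further objection is that 1 point is a sample-size target taken from a cited study, not a justified margin below which benefit is negligible. That also stands: a rule declaring no advantage whenever 1 point is excluded would do so in 20–34% of trials with a real 0.5-point benefit in one or both Exparel-containing arms.

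The gap itself remains. The protocol links a practice change to a finding it does not define, and the one analysis it specifies for means does not supply the estimate that the finding requires.

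**Conclusion.** The point holds as a gap between an anticipated conclusion and the planned analysis. The omnibus ANOVA remains a valid test of difference, and 40 per group is correct for it. What is missing is a pairwise estimate with an interval, and a statement of what a null result can and cannot show. The size depends on the true effect: the risk of an inconclusive result being taken as negative is substantial near 0.5 points and modest at 1 point. All figures assume variance 2, normal errors, equal arms of 40 and intervals not adjusted for multiplicity. A Tukey adjustment would widen the half-width from 0.63 to 0.75. Severity is minor to moderate.

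**What to change.** In Study Methodology, add that each Exparel-containing arm will be reported against bupivacaine as a mean difference with a 95% confidence interval, alongside the ANOVA.

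In Study Benefits to Virtua, add that a non-significant ANOVA alone will not be taken to show that Exparel lacks advantage. For a non-significant comparison:

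- if the interval includes a 1-point benefit, report the comparison as inconclusive;
- if it excludes 1 point, report only that a benefit of 1 point or more was ruled out, not that there is no benefit.

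Any stronger claim of no advantage should rest on a margin that the sponsor states and justifies in advance. A margin well below 1 point would need a larger trial.

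Apart from that stronger claim, the change costs a few sentences and no new patients or data. The downside is that some null results must be called inconclusive.

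### Means are compared without adjustment for extent of surgery, which the die roll does not balance; putting fusion and planned levels in a linear model would recover precision on pain at almost no cost.

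*Combined protocol and SAP*

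**What the plan says.** All references are to the combined protocol and SAP.

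- **Case mix.** Inclusion criterion 3 under Study Methodology admits "primary, 1 or 2 level, posterior lumbar laminectomy with or without fusion, discectomy with fusion, or fusion". The shares of each operation are not given.
- **Prognosis.** Background and Statement of Context lists reasons why spine surgery is painful, "including the size of the incision, the damage that may occur to ligaments, muscles, bone, discs, and joints when performing the surgical procedure". No size is given for this effect on any outcome.
- **Assignment.** Under Study Methodology, on the day of surgery "the circulating nurse will roll a die to randomly assign the patient to one of the three pain management groups", two faces of the die per group. Blocking, stratification and minimisation are not described. In the two groups that receive Exparel, the infiltration already differs by number of levels, so that number is known at assignment.
- **Sample size.** The inputs are "a target reduction in mean overall postoperative pain scores of 1 point on the VAS" and "our anticipated variance of 2", "for a statistical power of 80% and significance level of 0.05". The result is 40 per group, raised to 45 for dropout.
- **Analysis.** The last paragraph of Study Methodology plans ANOVA for means, chi-square tests for proportions and logistic regression for confounding. It names no covariates.

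**The concern.** The plan treats extent of surgery as a driver of pain and knows the planned operation beforehand, but uses this information neither in assignment nor in the primary comparison. Simple randomisation leaves the split of lighter and heavier operations across three arms of about 45 to chance.

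The confounding provision does not fill the gap. Logistic regression models a binary outcome; it could serve the incidence of opioid-related adverse events. It does not fit mean pain, opioid total, length of stay or time to therapy criteria. For the primary outcome the plan therefore has no usable adjustment.

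Two things are at stake. Case-mix variation that could be removed stays in the error term. And if the baseline table shows a visible gap in fusion share, no prespecified analysis answers the obvious question about it.

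**Working it through.** **Inputs from the protocol.** Difference 1 point, variance 2, alpha 0.05, power 80%, three arms, 40 evaluable and 45 enrolled per arm.

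**Assumptions, because the documents give no figures.** Share of patients with fusion p = 0.3 to 0.5. Extra pain with fusion D = 0.5, 1.0 or 1.5 points. The variance of 2 is taken as the total variance, case mix included. Only fusion is modelled; number of levels would act in the same way.

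**1. The plan's own figure.** One-way ANOVA, two means 1 point apart and the third midway (0, 0.5, 1). The noncentrality is λ = n × 0.5 / 2. At n = 40, λ = 10 and power is 0.805; at n = 39 it is 0.794. The stated 40 per group reproduces.

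**2. Size of chance imbalance.** The SD of the difference in fusion share between two arms is √(2p(1−p)/n). With n = 45:
- p = 0.3: √(0.42/45) = 0.097, 95% limits ±19 percentage points
- p = 0.5: √(0.50/45) = 0.105, 95% limits ±21 percentage points

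Simulating 135 die rolls 200,000 times gives these probabilities of a gap of 20 or more points:

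| Fusion share | One given pair of arms | Any two arms |
|---|---|---|
| 30% | 0.039 | 0.099 |
| 50% | 0.059 | 0.143 |

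A 20-point gap shifts the difference in mean pain by 0.20 × D, which is 0.1, 0.2 or 0.3 point. The standard error of a pairwise difference at 45 per arm is √(2 × 2/45) = 0.298.

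**3. Validity of the unadjusted test.** Simulated type I error of the one-way ANOVA under die-roll assignment (20,000 runs, p = 0.5) is 0.050 at D = 1. At D = 2, beyond the range used here, it is 0.047. The level holds.

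**4. Gain from adjustment.** Between-stratum variance is p(1−p)D², so residual variance is 2 − p(1−p)D² and λ = 40 × 0.5 / residual variance.

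| D | p | Residual variance | λ | Power at 40 per arm |
|---|---|---|---|---|
| none removed | – | 2 | 10.0 | 0.805 |
| 0.5 | 0.3 | 1.9475 | 10.27 | 0.816 |
| 0.5 | 0.5 | 1.9375 | 10.32 | 0.818 |
| 1.0 | 0.3 | 1.79 | 11.17 | 0.849 |
| 1.0 | 0.5 | 1.75 | 11.43 | 0.857 |
| 1.5 | 0.3 | 1.5275 | 13.09 | 0.902 |
| 1.5 | 0.5 | 1.4375 | 13.91 | 0.920 |

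These figures assume balanced strata, so they are upper values for a trial that keeps the die.

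**5. Where the gain comes from.** Simulated power with 120 patients and 50% fusion (Monte Carlo error about half a percentage point; ranges cover separate simulations):

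| D | Die, unadjusted | Die, fusion as factor | Stratified, fusion as factor |
|---|---|---|---|
| 1.0 | 0.79-0.80 | 0.84-0.85 | 0.86 |
| 1.5 | 0.80 | 0.91 | 0.91-0.92 |

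The model does most of the work; stratified assignment adds about a point or two.

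**6. What a realised gap does.** Take two arms of 45, p = 0.5, a 20-point gap and no treatment effect. The unadjusted comparison rejects beyond ±1.96 × 0.298 = ±0.584. The estimate centres on 0.2 × D with SE √(2 × (2 − 0.25D²)/45).
- D = 0.5: centre 0.1, SE 0.293, rejection about 6%
- D = 1.0: centre 0.2, SE 0.279, rejection about 9%
- D = 1.5: centre 0.3, SE 0.253, rejection about 13%

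This is a normal approximation. Averaged over all randomisations, the rate returns to 5%.

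**The case against.** The strongest reply is that simple randomisation of 135 patients is legitimate. Chance imbalance is not bias, the variance of 2 already contains case-mix variation, and the sample size already pays for it. All of that stands. A reader might infer that the die roll invalidates the comparison or biases the pain result; step 3 shows that it does not.

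A reader might also infer that imbalance moves every outcome by a material share of its target. The documents do not support that. Only pain has a target, and no prognostic effect is given for opioid dose, length of stay, time to therapy criteria, cost or adverse events.

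The size for pain is assumed too. If fusion adds only 0.5 point, power reaches at most 0.818. Rescue opioids given as needed could narrow pain differences between lighter and heavier operations. The 10-14% figure is a maximum over three pairs; for one given pair it is 4-6%, and the resulting shift of 0.1 to 0.3 point is about one standard error at most.

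Finally, a die is unpredictable, whereas blocks within four strata at one hospital with an unblinded surgical team are partly predictable. That is a real trade-off, and a reason to put adjustment first and stratification second.

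The objection does not rescue the analysis. A planned confounding analysis exists, but its method cannot be applied to the primary outcome.

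**Conclusion.** The point holds as one of efficiency and credibility, not of validity. The primary comparison ignores a prognostic factor that the protocol itself names and knows in advance, and the planned confounding method does not fit the continuous outcomes. With fusion in 30-50% of patients, adjustment would lift power at 40 per arm from 0.80 to at most about 0.82, to 0.85-0.86 or to 0.90-0.92 for an added 0.5, 1.0 or 1.5 points. The size of the gain rests entirely on those assumed shares and effects. The direction does not, provided that extent of surgery affects pain as the Background says.

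A reader might credit the whole gain to replacing the die. The calculation does not support that: most of it is available with the die kept.

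**What to change.** **Main change.** Prespecify a linear model (ANCOVA or multi-factor ANOVA) with treatment arm, fusion (yes/no) and planned levels (1/2) for mean pain, opioid total, length of stay and time to therapy criteria. Use the operation as planned before assignment. Drop logistic regression for these outcomes and keep it for binary ones, with the same covariates named. The cost is a few sentences in the analysis paragraph. It needs no extra patients, and both factors are known before surgery.

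**Secondary change.** Replace the die with a concealed, computer-generated list with varying block sizes, stratified by the same two factors, as numbered sealed assignments opened in the operating room. Amend the description of the die that patients are given at consent. This adds visible balance and an allocation record; none is described for the die. The cost is preparing the list once and a small amendment, plus some block predictability with an unblinded surgical team, which varying block sizes reduce.
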